During the conduct of clinical research with human participants for this study, there is the potential that an acute opioid risk situation will arise. For this study, this situation can include subjects who mention or endorse opioid use habits that acutely increase their risk of an overdose, or experiencing an overdose within the last 30 days. The following guidelines are designed to support project personnel in the management of these acute opioid risk situations. Specifically, these policies and procedures are designed to assist project personnel with identifying and contacting the health care agencies/resources that are the most appropriate for providing support in these specific instances. In all acute situations, project personnel should contact project managers and PIs as soon as possible, so that they can assist in the management of the situation.

Participants expressing acute overdose risk during an interview, or in response to a questionnaire will be assessed regarding risk level. We will use the same procedures described above for addressing on-line survey responses that indicate potential overdose risk. Based on the participants’ responses, research staff will focus on recent experiences (past 30 days) to assess current overdose risk level. Research staff will remind the participant of the exclusions to confidentiality that were covered in the informed consent process, and at the beginning of each assessment. Example consent language may include: “For this study, exclusions to confidentiality include child or elder abuse, harm to others or harm to yourself. Harm to yourself can include thoughts of suicide or using opioids in a harmful way. If any of these situations were to come up, we would talk to you more about it and may help you get in touch with others, including your provider or other authorities, to make sure that you are safe.” Participants will be encouraged to disclose aberrant opioid use or concurrent substance use with opioid prescription to their healthcare provider. Participants who are determined to be at a low or moderate risk for overdose will be provided with an overdose safety brochure with information on how to access naloxone. Research staff will encourage participants to talk to their current treatment providers or clinicians about their substance use. For

those participants who are no longer receiving treatment services, participants will be encouraged to re-engage in care and will be provided with a list of available treatment programs and resources that may be available to them. For participants who are determined, after the risk assessment, to be at high imminent risk for an overdose or are actively experiencing a substance-related crisis, research staff will contact 911 immediately. Research staff will remain with the participant until help arrives. All emergency actions as well as risk assessments conducted will be documented and reviewed by the PIs to ensure all safety protocols were followed.

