In each case, the research personnel will follow the suicide risk assessment protocol (see section 7.2 “Methods and Timing for Assessing, Recording, and Analyzing Safety Parameters” and the study Data and Safety Monitoring Plan) and consult with the PIs to determine whether the participant’s distress was significant enough to warrant reporting as an AE.

(7) **Psychological discomfort** as a result of being asked personal questions, particularly during the assessments and sessions. Participants may also become anxious or upset during discussions of their thoughts about issues such as their mental health treatment that occur during the sessions.

Study staff will be trained to respond to this discomfort, including receiving extensive crisis training and proper ways to refer participants to appropriate resources (i.e., treatment center staff, authorities, etc.) as necessary. Additionally, to minimize this risk, all participants will be informed of their right to refuse to answer any question they do not wish to answer and of their right to withdraw from the study at any time. Participants will also be informed that they can take breaks. There is a small risk that the PPMI and EUC conditions might upset participants. EUC sessions will focus on providing beneficial educational materials and participants will have opportunities to express and discuss any distressing thoughts or emotions these materials produce. The PPMI condition will utilize a CBT-based intervention. CBT for pain management approaches have established efficacy to improve pain-related functioning and it has been the experience of the project's investigators that these approaches dramatically diminish risks to participants from the study's intervention. Study therapist delivering both conditions will be masters-level therapists and will receive regular supervision by the [name], who is a licensed psychologist, or other specified staff member/clinical supervisor. They will also receive intensive training in dealing with high risk patients.

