- (1) We will have an additional screen/page pop up for any participant who flags for suicide risk (e.g. endorses anything other than "not at all" on the PHQ item #9 asking about "thoughts that you would be better off dead, or of hurting yourself in some way" and/or endorses an overdose in the past 30 days on overdose history item #3 and indicates on item #7 the overdose was "on purpose, I wanted to die" or "I didn't want to die, but didn't care about the risks). The page will contain contact information for national and international suicide hotlines and web links to crisis centers. We will also include the study telephone number for non-emergencies. The URLs in the page open in a different window so the survey is not interrupted. These resources (and the health brochure) may be included in our study correspondence (i.e., letter, e-mail) regardless of risk level.
- (2) The page will stay open for a minimum time period in attempts to assure the participant has read the information. The participant will not be able to close out of the survey until they check a box that indicates they have read and understand the information presented to them. This will confirm that the participant has viewed the information.
- (3) REDCap will auto generate an email to the study team indicating "flagged" cases after the survey has been submitted. The email will have only the study ID.
- (4) At least three attempts will be made to reach the participant by phone within 72 hours to further assess level of risk and/or answer questions. If the participant does not respond to research staff contacts attempts, the PIs will determine the appropriate course of action needed based on the risk level and situation.

Surveys completed via **postal mail** (we expect that this will be a very rare occurrence) may include the resource brochure which includes national suicide hotlines and mental health services. Surveys that are returned in which the participant endorses anything other than "not at all" for PHQ item #9 asking about "thoughts that you would be better off dead, or of hurting yourself in some way", endorses an overdose in the past 30 days, item #3 of the overdose history questions, and

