indicates on item #7 “on purpose, I wanted to die” or “I didn’t want to die, but didn’t care about the risk,” or that indicate suicidal ideation or harm to others will be contacted by study staff. Study staff will make at least three attempts to reach the participant by phone within 72 hours of receiving the survey to further assess level of risk and/or answer questions. If the participant does not respond to research staff contacts attempts, the PIs will determine the appropriate course of action needed based on the risk level and situation.

In addition to suicide risk, all research staff will also be trained and prepared for situations in which a participant not currently in treatment reports severe substance misuse, for example if the participant has recently experienced increased substance use plus an emergency substance-related situation requiring immediate medical care (e.g. overdose) within the past 30 days. Our protocol in this regard is based on previous research that developed and implemented human subjects’ protections termed “rescue treatment” or “protective transfer” in studies of people with substance use disorders receiving less than standard treatment or having a poor response to standard or experimental treatments. In our study, participants who report at follow-up (during an interview or self-report measure) that they were hospitalized or made an emergency room or acute care outpatient visit due to acute substance use within the past 30 days will be protected by having project staff conduct a brief risk assessment and provide them with a resource brochure with local substance abuse resources and/or a referral to substance abuse treatment. Participants who require rescue treatment or immediate medical attention will be referred to the hospital or treatment provider closest to where they are residing. If the nearest facility is rejected by the participant for any reason, project staff will utilize SAMHSA’s online substance abuse treatment facility locator to provide a list of appropriate services.

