7.2 Methods and Timing for Assessing, Recording, and Analyzing Safety Parameters

All participants will be monitored for safety issues during their participation at all study visits, including condition sessions. Research study staff will be trained to identify and review all measures denoted as ‘risk flags’ prior to ending the assessment with a participant (or following completion of the online assessment). All participants who flag for an increase in risk to safety will be assessed by staff immediately after learning of the risk. Participants will be notified of the need for any consult with clinical supervisors should it arise. All incidents where increased risk was identified according to the parameters listed in section 7.1, or where risk was spontaneously generated by the participants during a study visit, will be documented using the study specific Risk Assessment Note. Routinely, the project managers will meet with PIs to analyze the Risk Reporting Forms to observe any patterns in participant risk status.

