During this study, the major potential risk to study participants is violation of confidentiality of qualitative interview and assessment data. The risk of violation of confidentiality exists because participants will be disclosing personal information in assessments and intervention sessions. This risk is related to the damage that could be caused by an inadvertent release of sensitive information (e.g., substance use, medical conditions). Participants will be informed of the procedures taken to protect their confidentiality. There is also a slight risk of psychological discomfort to study participants as a result of being asked personal questions on sensitive topics. Participants may also become anxious or upset during discussions of their thoughts about managing their pain or substance use during the condition sessions and/or the assessments. Study staff will be trained to respond to this emotional distress and to refer participants to appropriate resources, as necessary. All participants will be free to terminate the assessments at any time or refuse to respond to any questionnaire item. All information collected is for research purposes only, and data will be kept in strict confidence. Under the 21st Century Cures Act, this study is covered by a Certificate of Confidentiality from NIH. Drs. [name] and [name] will ensure that all relevant IRBMED policies, procedures, and stipulations are being

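### For self-completed online assessments, the visible protocol describes an automatic staff alert for a suicide or overdose flag only once the survey is submitted, so a flagged answer in a survey left part-way has no described alert

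*Combined protocol and SAP*

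**What the plan says.** Section 7 (Safety Assessments) gives four steps for online answers that suggest suicide risk.

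- Step 1: a page of crisis resources opens when a participant flags.
- Step 2: the page must be acknowledged: "The participant will not be able to close out of the survey until they check a box that indicates they have read and understand".
- Step 3: REDCap e-mails the study team about flagged "cases after the survey has been submitted".
- Step 4: "At least three attempts will be made to reach the participant by phone within 72 hours to further assess level of risk".

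The acute opioid risk text in the same section extends this to overdose: "We will use the same procedures described above for addressing on-line survey responses that indicate potential overdose risk".

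Section 7 also requires staff to go over the self-report risk measures before a participant departs from an assessment or a session ends. Section 7.2 sets the time of flag review as "prior to ending the assessment with a participant (or following completion of the online assessment"), and says that a flagged participant is assessed immediately once staff know of the risk. Section 7.1 ties the risk assessment to the response: any non-zero answer on PHQ-9 item 9, or an overdose in the past 30 days on item 3 of the overdose questions, with item 7 adding a suicide assessment. These items are given at baseline and at 1, 3, 6, 9 and 12 months.

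**The concern.** Section 7.1 names suicide and increased substance use or overdose as the main safety concerns in this population, and its trigger is the answer. The online route by which staff hear of that answer has a different trigger, submission of the survey. The two coincide when a survey is finished in one sitting. They separate when it is not.

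Unfinished surveys are foreseeable. Section 6.2.2 allows the baseline survey by e-mailed link, section 6.2.4 allows follow-up online, and section 10.2 describes completion on the participant's own device. Section 6 expects about 2 hours at baseline and 90 minutes at follow-up, interview included, and describes splitting an assessment across days when a participant tires. Section 7 adds: "Participants will also be informed that they can take breaks". Section 11.3 adds: "All participants will be free to terminate the assessments at any time or refuse to respond to any questionnaire item".

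At stake is whether staff learn promptly that someone has reported suicidal thoughts or a recent overdose and then stopped.

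**Working it through.** No arithmetic applies. The check follows one case through each rule: a participant alone at home gives a non-zero answer on PHQ-9 item 9, acknowledges the crisis page, and stops without submitting.

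1. **Crisis page (section 7, steps 1 and 2).** It opens and is acknowledged. It informs the participant. Nothing says that it notifies staff, and ticking its box is not described as submission.
2. **Automatic e-mail (step 3).** Its stated time is after submission. The survey has not been submitted, so no e-mail is described.
3. **Phone attempts (step 4).** These follow the e-mail in sequence, so without it nothing starts them.
4. **Staff review before departure (section 7).** This rule is tied to risk measures and is the most relevant safeguard. It works when staff are present or on the line. No mechanism is stated for a remote survey left part-way.
5. **Online flag review (section 7.2).** It is placed after completion, and this assessment is not complete.
6. **Immediate assessment (section 7.2).** It is counted from when staff learn of the risk, so it depends on items 2 to 5.
7. **Other contacts.** The researcher interview (section 6.2), the follow-up efforts (section 6.2.4) and the check of incomplete forms (section 10.3.3) may bring the answer out. None is tied to a risk flag or has a risk-based deadline.
8. **Duty to assess (section 7.1).** It already applies, because it attaches to the response.

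At item 8 the protocol calls for an assessment, and at items 2 to 7 no described rule ensures that staff know it is due. The overdose items follow the same path.

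**Size.** The number affected would be the number of administrations multiplied by three shares: self-completed online, flagged, and left unsubmitted. None of the three is given. A count of all scheduled administrations would not bound the problem usefully. It would include staff-led assessments, and section 6.2.4 prefers in-person follow-up where possible. It would also include the baselines of randomized participants, whose baseline data collection must be complete before randomization (section 6.2.2). No count or delay is therefore offered.

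**The case against.** The strongest reply is that the gap may not exist outside the visible text. Section 4.2 refers to the DSMP, the MOP and the standard operating procedures for further safety detail, and the suicide flowchart for all assessments in Appendix A is not reproduced. This stands as a limit: the supported statement is that no such alert is described, not that none exists. The flag items may also already sit in a survey of their own, since section 10.2 speaks of REDCap surveys in the plural.

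A reader might infer more than the documents support in four ways:

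- *That a flagged person is left without help.* The crisis page opens within the survey, and section 7 does require staff review of risk measures. What is missing is a stated way for that review to reach a remote partial survey.
- *That step 2 lets people leave once the box is ticked.* The text makes the tick necessary for closing. It does not say that it is sufficient, and the page order is not given.
- *That the 72-hour period is defective because step 4 names no start.* The postal rule does name one: "Study staff will make at least three attempts to reach the participant by phone within 72 hours of receiving the survey". But step 4 directly follows the e-mail in step 3, so the start is clear enough from sequence. This is a wording clarification only.
- *That staff should plainly be alerted to any saved answer, submitted or not.* This is debatable. It means contacting people about answers that they chose not to submit, which sits uneasily with the freedom to stop in section 11.3. Waiting for submission, alongside an immediate crisis page, is a defensible choice. This is why the main fix below keeps submission as the trigger.

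**Conclusion.** The point holds in a limited form. For self-completed online assessments, the visible protocol describes an automatic staff e-mail only after submission and flag review only after completion. A flagged answer in an unsubmitted survey brings up the crisis page but no described automatic alert, although section 7.1 calls for a risk assessment on that answer. Steps 3 and 7.2 agree with each other, so this is not a contradiction between them. It is a case that neither covers.

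The number affected is unknown, and nothing here bears on the primary outcome, power or error rates. Confidence is medium, because the conclusion assumes that the DSMP, MOP and flowcharts contain no finer trigger and that the flag items are not already submitted separately. If either assumption fails, one sentence in section 7 saying so would settle the matter. Otherwise this is a low-cost safety improvement that the sponsor should make.

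**What to change.** **Section 7, online procedures.** State that *PHQ-9 item 9 and overdose items 3 and 7 are given in a short REDCap survey, submitted on its own before the remaining measures, and the step 3 e-mail is sent when that survey is submitted.* The existing rule then fires at once, whether or not the rest is finished. The overdose text follows because it uses the same procedure. To keep the instruments intact, the whole PHQ-9 and overdose block can go in this short survey.

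**Section 7.2.** Tie online flag review to *receipt of the flag e-mail, whether or not the rest of the assessment is complete*.

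**Cost.** A small change in survey layout and item order, two protocol sentences, and the approvals that sections 10.1 and 11.1 require for data forms and amendments. Some alerts will concern answers later clarified. A participant who leaves within the short survey itself would still raise no alert, but the exposure shrinks to a few items. Because the trigger remains a submitted answer, no new consent wording is needed for unsubmitted ones.

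**Optional.** An alert when a flagged page is saved would close that remainder. It needs consent or pop-up wording that staff may call about an unsubmitted answer, agreement of both the University of Michigan and VA Ann Arbor IRBs, and possibly re-consent (section 6.2.1). The documents do not say whether the REDCap set-up supports it. Naming the e-mail as the start of the 72 hours in step 4 is a harmless clarification.

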7.1 Specification of Safety Parameters

Participants will be assessed for safety concerns throughout the study. The main safety concerns expected for this population revolve around risk of suicide and risk of increased substance use or overdose. All participants will receive a resource brochure at each study visit that will include information regarding substance use, warning signs of suicide, and resources and safety tips related to reducing overdose risk. This information is also available on the study website and a link to the information will be provided in all study correspondence. Specific questions will be asked of participants at each assessment that will evaluate risk and will trigger when an additional risk assessment will be conducted by research staff. These include the following:

- **Patient Health Questionnaire (PHQ-9)** (*administered at Baseline, 1-, 3-, 6-, 9-, and 12-month follow-up*)
 - Any participant who indicates a response greater than Zero (“Not at all”) e.g. a “1”, “2”, or “3”, on item #9 which states “Thoughts that you would be better off dead, or of hurting yourself in some way” will be assessed for suicide risk.
- **Overdose History Questionnaire** (*administered at Baseline, 1-, 3-, 6-, 9-, and 12-month follow-up*)
 - Any participant who indicates a response of “within the past 30 days” on item #3 which states “When was the most recent time you took too much drugs or medications/pills?” will be assessed for acute overdose risk.
 - In addition to #3 marked “within the past 30 days”, a participant who indicates on item #7 a response of “on purpose, I wanted to die” or “I didn’t want to die, but I didn’t care about the risks” will be assessed for suicide risk.

7.2 Methods and Timing for Assessing, Recording, and Analyzing Safety Parameters

All participants will be monitored for safety issues during their participation at all study visits, including condition sessions. Research study staff will be trained to identify and review all measures denoted as ‘risk flags’ prior to ending the assessment with a participant (or following completion of the online assessment). All participants who flag for an increase in risk to safety will be assessed by staff immediately after learning of the risk. Participants will be notified of the need for any consult with clinical supervisors should it arise. All incidents where increased risk was identified according to the parameters listed in section 7.1, or where risk was spontaneously generated by the participants during a study visit, will be documented using the study specific Risk Assessment Note. Routinely, the project managers will meet with PIs to analyze the Risk Reporting Forms to observe any patterns in participant risk status.

7.3 Adverse Events and Serious Adverse Events

For this study, we will utilize definitions for adverse events (AEs) and serious adverse events (SAEs) based on the University of Michigan IRBMED guidelines and definitions as follows:

- **Adverse Event (AE):** An adverse event (AE) is any experience or abnormal finding that has taken place during the course of a research project and was harmful to the subject participating in the research, or increased the risks of harm from the research, or had an unfavorable impact on the risk/benefit ratio. The event may or may not be caused by an intervention (e.g., headache following spinal tap, death from the underlying disease, car collision). Adverse Events also include psychological, social, emotional, and financial harms.
- **Unanticipated Problems (UP):** Unanticipated problems involving risks to subjects or others include, in general. For an event or information to be considered an “unanticipated problem,” three criteria must be met:
 - It must be “**unanticipated.**” This means the event is **not** expected in terms of its nature, severity or frequency given the:
 - Procedures described in the study documents (e.g. the application, protocol, data and safety monitoring plan, etc.)
 - Characteristics of the subject population being studied (the traits, behaviors, symptoms, diseases, life experiences, or other qualities typically found in the persons comprising those eligible to participate in the study). A UP is a problem that was expected by neither the research participants nor the investigators (Note: This is not the same as the FDA definition of "unexpected")
 - It must be “**related to the research.**” This means there is a reasonable possibility that the event or information may have been caused by, or is linked in a significant way, to the research. This encompasses all aspects of the research; it is not limited to test agents or procedures. It is also not necessarily limited to actions of the UM investigators.
 - The event or information suggests that the research places subjects or others at greater risk of harm than was previously known or recognized. This includes physical, psychological, economic, or social harm:
 - Type 1: Potential harm - Possibility that previously unsuspected harm may occur (or may occur at a higher than expected rate) even though no one has yet experienced actual harm.
 - Type 2: Actual harm - Recognized harmful or unfavorable outcome that has actually occurred to a research subject, a set of subjects, another individual being treated in a similar fashion in a relevant non-research setting, or another person connected to the research study.
- **Serious Adverse Event (SAE):** A serious adverse event (SAE) is one that meets one or more of the following criteria:
 - Results in death
 - Is life-threatening (places the subject at immediate risk of death from the event as it occurred)

- Results in inpatient hospitalization or prolongation of existing hospitalization
- Results in a persistent or significant disability or incapacity
- Results in a congenital anomaly or birth defect

An important medical event that may not result in death, be life threatening, or require hospitalization may be considered an SAE when, based upon appropriate medical judgment, the event may jeopardize the subject and may require medical or surgical intervention to prevent one of the outcomes listed in this definition.

